In addition, the investigator or designee will instruct the participant to call immediately if the selected contraception method is discontinued and document the requirement to use an alternate protocol-specified method, including if the participant will no longer use abstinence as the selected contraception method, or if pregnancy is known or suspected in the participant or partner.

Study Design

Baseline: After recruitment, consent form completion, and screening examination within 30 days of consent, eligible participants (determined after review of the 2-week run in diary) will undergo a colonic transit measurement with scans at 6-8, and 24 hours. After the 24 hr image is obtained, participants will undergo rectal compliance and sensation study. These baseline tests will take up to 2 days.

Clinical Trial: This is a prospective, randomized placebo-controlled trial of rimegepant in participants with non-constipation IBS and chronic abdominal pain where 24 have started their assigned treatment. The randomization schedule will be generated by Pfizer and communicated to the research pharmacy, with the study participants and investigators blinded. Allocation to treatment will be concealed from all participants and investigators. Randomization and delivery of study medication through the clinical research trials unit will occur after the performance of the baseline colonic transit, and rectal sensation and compliance testing. The trial period will consist of a two-week run-in period (before presenting to the clinical research trials unit for the baseline testing), and a 4-week (28-32 days) treatment period. Participants will fill a daily diary regarding abdominal pain, stool consistency and bowel function. They will also complete questionnaires that survey anxiety and depression and IBS-QOL during the screening period and at the end of the 4-week (28-32 days) trial. The final washout phase is a total of 4 weeks, during which the daily diary is continued for 28 days which includes the following questionnaires: Daily Abdominal Pain, Bloating, Flatulence, and Urgency Scores by VAS, Daily Bowel Diary including Bristol Stool Form Scale, and the Likert Scale Questionnaire for Most Intense Pain (0-4) The IBS Quality of Life Questionnaire and Hospital Anxiety Depression Questionnaire will be completed at the end of 4 weeks after the last dose of study medication.

SCHEDULE OF ASSESSMENTS

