The covariates to be considered for inclusion in the ANCOVA models for colonic transit are gender, BMI, HAD scores (anxiety and depression scales), the BDQ Somatic Symptom Checklist (SSC) score. These will be considered for inclusion by checking plots of residuals (from the ANCOVA models) against these scores. The analysis will compare colonic transit between the two treatment groups.

Gastric Emptying

Given the reports of nausea and vomiting in participants with migraine as well as observations of these symptoms during clinical trials of CGRP receptor antagonists, we will also measure gastric emptying $T_{1/2}$ (minutes) and proportion emptied at 4h (%) at the end of 4 weeks treatment and compare the results for the active treatment group to those of the placebo group. Sex and BMI will be considered as co variates in this analysis.

Sensory Ratings

The assessment of phenotype associations with observed sensory ratings (rectal sensation VAS scores) will be based on analysis of covariance (ANCOVA) for repeated measures (the four phasic distension levels). Each type of VAS score will be analyzed individually (first sensation, gas, urgency, and pain). The covariates to be included in the ANCOVA models for each VAS score were age, sex, BMI, the “tiredness”, “peace”, “worried”, and “activity” VAS scores, the HAD scores, and the BDQ SSC score. Though most of these scores may not be significant covariates in these models, due to the nature of the responses, it is appropriate to include them. In addition, the corresponding pressure (12, 24, 30, 36 mmHg) at each phasic distension level (the repeated factor) is included in each of these ANCOVA models along with the main effect term for phenotype (e.g. age, sex, BMI), and the 2-way interaction term for phenotype by pressure.

Sensation pressure thresholds

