A “time to event” approach (i.e. pressure required to evoke specific sensations) will be used to assess four sensation thresholds (first desire to defecate, gas, urgency, and pain). Since some threshold levels are “censored” (e.g. pain not evoked by the maximum distension pressure used according to the protocol approved by the IRB), a Kaplan-Meier summary of the pressure thresholds will be used to univariately depict the cumulative probability of evoking the sensation, and proportional hazards regression models will be used to assess group effects separately for each of the sensation types. The same covariates listed above used in the analyses of sensation VAS ratings will be included in the proportional hazards regression models, in particular the ratings of “tiredness”, “peace”, “worried”, and “activity” recorded during the sensation studies.

Rectal compliance

The covariates included in the ANCOVA models for fasting colonic tone and compliance $Pr \frac{1}{2}$ values will be age, gender, BMI, the “tiredness”, “peace”, “worried”, and “activity” scores, the HAD scores, and the BDQ somatic symptom score.

Endpoints

Primary Endpoint

is abdominal pain scores in participants with non-constipation IBS

Summary of Secondary Endpoints will be focused on characterizing rectal compliance and sensation, and colonic transit,

The *secondary endpoints* for analysis will be:

- a. Colonic transit geometric center at 24 hours
- b. Colonic transit geometric center at 48 hours
- c. Gastric emptying of solids $T_{1/2}$ (minutes) and % emptied at 4h
- d. Rectal compliance
- e. Rectal sensation during ascending method of limits
- f. Rectal sensation during random order, graded phasic distensions
- g. IBS-QOL
- h. Safety/adverse effects

Sample Size

This study is meant to be a pilot study that will provide preliminary information regarding the usefulness of treating participants chronic abdominal pain associated with non-constipation IBS with rimegepant.

The estimated effect size (with $n=12$ per treatment group) for each of the primary and secondary endpoints is based on power calculation using data acquired from patients with IBS-D at Mayo Clinic^{56, 57}.

Table 4. Key Gastrointestinal Physiologic Data in 163 People Based on Bowel Function Subgroup

	Healthy controls	IBS-C	IBS-D	IBS-M
Number of males	41 (0)	49 (0)	44 (3)	29 (0)
Fasting gastric volume, mL	226 ± 11	229 ± 11	247 ± 11	222 ± 12
Postprandial gastric volume, mL	736 ± 13	740 ± 14	735 ± 14	770 ± 17

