Δ postprandial fasting gastric volume, mL	511 ± 13	525 ± 12	488 ± 12	548 ± 19 ^a
Proportion of GE at 2 h	0.47 ± 0.02	0.49 ± 0.02	0.45 ± 0.02	0.42 ± 0.03
GE, T1/2, min	126.0 ± 4.4	126.8 ± 4.7	135.5 ± 5.6	137.6 ± 6.0
Satiation: maximum tolerated volume, mL	1028 ± 44	1044 ± 40	1046 ± 45	1106 ± 81
Satiation: aggregate symptom score	158 ± 14	186 ± 10	188 ± 12	184 ± 16
Colonic filling at 6 h, %	48 ± 5	54 ± 4	56 ± 3	44 ± 5
Colon transit GC 24 ^b	2.35 ± 0.16	2.03 ± 0.10	3.03 ± 0.19	2.34 ± 0.10
Colon transit GC 48 ^c	3.23 ± 0.18	3.0 ± 0.13	4.14 ± 0.17	3.94 ± 0.16
Rectal compliance, Pr _{1/2} , mm Hg	12.6 ± 0.8	12.5 ± 0.8	14.2 ± 0.6	14.0 ± 0.9
Threshold for first sensation, mm Hg	7.8 ± 0.5	7.8 ± 0.7	8.4 ± 0.7	8.1 ± 0.8
Threshold for gas, mm Hg	13.8 ± 1.5	14.0 ± 1.2	13.3 ± 1.2	14.5 ± 1.6
Threshold for pain, mm Hg	29.1 ± 2.1	29.0 ± 2.0	31.0 ± 1.8	31.0 ± 2.2
Threshold for urgency, mm Hg	17.5 ± 1.1	20.5 ± 1.6	18.8 ± 1.4	17.4 ± 1.2
Sensation rating, pain 30 mm Hg	55.1 ± 4.5	52.5 ± 4.6	55.3 ± 4.2	54.3 ± 5.6
Sensation rating, urgency 30 mm Hg	74.9 ± 2.8	71.5 ± 3.3	74.4 ± 2.5	74.3 ± 3.1

NOTE. There were 41 controls and 122 patients with IBS (data are mean ± SEM). For the number of participants undergoing each measurement, see the Methods section.

^aP = .017 versus healthy controls.

^bOverall P < .001.

^cOverall P < .001.

In a prior study that evaluated abdominal pain scores on a daily diary 0-100 mm for severity of abdominal pain, patients with IBS had the following pain severity at baseline prior to treatment (Pain, 100-mm VAS 37.2 (27.1–49.5) (57)

parameter	Mean	SD	Effect size (absolute and % of mean), 80% power; α=0.05
Average pain score on 0-100mm VAS	37.2	11	13.16 (35%)
Colonic transit GC24	3.03	1.25	1.5 (50%)
Colonic transit GC48	4.14	1.12	1.34 (32%)
Rectal compliance	14.2	3.94	4.7 (33%)
Threshold for first sensation	8.4	4.59	5.5 (65%)
Threshold for gas	13.3	7.87	9.4 (71%)
Threshold for pain	31	11.81	13.3 (43%)
Threshold for urgency	18.8	9.18	11 (59%)
Sensation rating pain 30 mmHg	55.3	27.55	33 (60%)
Sensation rating urgency 30mm Hg	74.4	16.4	19.6 (26%)
Gastric emptying T1/2	135.5	36.7	44 (32.6%)
Proportion of gastric emptying at 4h	0.45	0.13	0.156 (34.7%)

FEASIBILITY AND TIME FRAME

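### Ten forced covariates for 24 participants cost the compliance model much of its stated power and inflate false positives in the threshold models, while each endpoint's own baseline is left out

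*Combined protocol and SAP*

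**What the plan says.** All places are in the combined protocol and SAP, Statistical Analysis, unless stated.

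- **Sensory Ratings.** A repeated-measures ANCOVA over four pressures includes age, sex, BMI, four mood scales (tiredness, peace, worried, activity), the HAD scores and the somatic symptom score. Colonic Transit names two HAD scales, so the count is 3 + 4 + 2 + 1 = 10. On whether they matter: "Though most of these scores may not be significant covariates in these models, due to the nature of the responses, it is appropriate to include". The main effect is called phenotype, with age, sex and BMI as examples. No treatment term is named.
- **Sensation pressure thresholds.** "The same covariates listed above used in the analyses of sensation VAS ratings will be included in the proportional hazards regression models".
- **Rectal compliance.** The sentence that begins "The covariates included in the ANCOVA models for fasting colonic tone and compliance" lists the same ten.
- **Colonic Transit.** "The covariates to be considered for inclusion in the ANCOVA models for colonic transit are gender, BMI, HAD scores" and the somatic symptom score. These are candidates only, to be judged from residual plots.
- **Gastric Emptying.** Measured "at the end of 4 weeks treatment and compare the results for the active treatment group to those of the placebo group". Sex and BMI are to be considered.
- **Sample Size.** "The estimated effect size (with $n=12$ per treatment group) for each of the primary and secondary endpoints is based on power calculation". The table's effect column is headed with "80% power; α=0.05". Study Design describes a trial "where 24 have started their assigned treatment".

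Study Design places randomisation after baseline transit and barostat testing. The Schedule of Assessments repeats both at end of treatment. Baseline adjustment is mentioned only for the pain diary score, under Clinical Data.

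**The concern.** Ten forced covariates plus treatment is a large model for 24 participants. Each covariate costs a degree of freedom, and its chance imbalance between arms widens the standard error of the treatment effect. A covariate repays that only if it explains outcome variance, and the plan itself doubts that most will. In a proportional hazards model with so few events the problem is different: the test no longer holds its nominal level.

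The mood scales are completed at each barostat session, and the thresholds section refers to ratings recorded during the sensation studies. For the end-of-treatment comparison the natural reading is that post-randomisation values are used, and nothing restricts them to baseline.

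The covariate most likely to help, the same measure before treatment, is in none of the lists. Rectal compliance and sensation are secondary aims 1 and 2, and the pilot is meant to give an early efficacy signal and variance estimates for a later trial. A compliance effect could be missed, and a threshold effect could be spurious.

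**Working it through.** **Inputs.** n = 12 per arm, alpha 0.05, power 80% (Sample Size); sidedness is not stated, so two-sided is assumed. Means and SDs are from the effect-size table. The ramp runs in 4 mm Hg steps to 60 mm Hg and stops at pain (Ascending method of limits). No dropout rate is given; all 24 are taken as evaluable, the best case.

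**1. Reproduce the table.** For an unadjusted t test the noncentrality is d × √(n/2) on 22 df. Power of 80% needs d = 1.197, that is 1.197 × √6 = 2.93.
- Compliance: 1.197 × 3.94 = 4.72 (table 4.7).
- Pain rating: 1.197 × 27.55 = 32.98 (table 33).

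Eleven of the 12 rows give 79.7–80.2% power. The exception is the pain threshold: 1.197 × 11.81 = 14.1 against a tabulated 13.3, which has 75% power.

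**2. Compliance with 10 covariates.** Residual df = 24 − 2 − 10 = 12. For covariates that differ between arms only by chance, the expected variance inflation is (N − 3)/(N − 3 − 10) = 21/11 = 1.91. If they explain a share R² of the within-arm variance, the noncentrality is roughly 2.93/√(1.91 × (1 − R²)). Averaging power over the random imbalance gives:

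| R² | Power at the tabulated effect |
|---|---|
| 0 (unadjusted test) | 80% |
| 0 | 52% |
| 0.1 | 56% |
| 0.2 | 61% |
| 0.3 | 66% |
| 0.4 | 72–73% |
| 0.5 | 79% |

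Break-even is at R² of about 0.50. With R² = 0 the effect detectable with 80% power rises from 1.20 to about 1.7 SD, or 1.7 × 3.94 = 6.7 mm Hg instead of 4.7.

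**3. Sensory ratings.** The same 10 between-participant covariates act in the same direction. The table row is for one pressure (30 mm Hg) and the model uses four, so the 52% does not carry over.

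**4. Threshold models.** Parameters: 10 + 1 = 11. Events: at most 24, so 24/11 = 2.2 per parameter. Simulation with no treatment effect: 24 participants, gamma-distributed thresholds with the table's means and SDs (pain, urgency, gas), 4 mm Hg steps, censoring at 60 mm Hg, the ramp stopping at pain, Efron ties, covariates unrelated to outcome, 1,000–2,000 runs per main scenario and about 600 for two and for eleven covariates.

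| Model | Null rejection at nominal 5% |
|---|---|
| Treatment only | 4–6% (Wald) |
| Treatment + 1 covariate | 5–7% |
| Treatment + 2 covariates | 7–8% |
| Treatment + 10 covariates | 14–18% (Wald), 15–20% (likelihood ratio) |
| Treatment + 11 covariates | 19–21% |

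**5. Own baseline as sole covariate.** Residual df = 21; variance factor 21/20 × (1 − r²) = 1.05 × (1 − r²). The documents give no baseline-to-follow-up correlation r, so a range is shown. Power at 1.197 SD is 82% (r = 0.3), 85% (0.4), 88% (0.5), 93% (0.6) and 97% (0.7).

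**The case against.** The affected endpoints are secondary in a self-described pilot. The primary pain comparison is a t test or rank sum test and is untouched. That stands, and it sets the severity.

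A covariate that is not significant can still explain some variance, so R² = 0 is the pessimistic end. That also stands, which is why the range is given. But recovering 80% needs about half the variance explained, which sits badly with the plan's own remark.

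The mood scales are taken before the sensation measurements, as markers of state during the test. That is a rationale. Distortion would require the drug to change mood, and the documents give no size for that. The objection to them is that they are measured after randomisation, not that a bias has been shown.

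A reader might infer that omitting baseline values is what pulls power below 80%. It cannot be, because the table is already unadjusted; the omission only forgoes a gain. Nor do the lists prove that no baseline term is intended: the transit text refers to ANCOVA models whose base terms are not stated.

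A reader might also apply 52% to every physiological endpoint. The transit and gastric-emptying covariates are only considered. If all were kept and unrelated to outcome, power would be about 68% (five covariates) and 76% (two). Finally, the inflated error rate concerns the proportional hazards models only; the ANCOVA tests keep their nominal level in theory.

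**Conclusion.** The concern holds for the rating, threshold and compliance models. For compliance, power at the tabulated effect is about 52% with unrelated covariates, 66% at R² = 0.3, and about 80% only near R² = 0.5. The ratings model loses precision by an amount that the table cannot fix. The threshold models have a Wald type I error of about 14–18% at nominal 5%, roughly three times what is claimed.

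These figures assume two-sided tests, 24 evaluable participants and covariates balanced between arms apart from chance; the Cox figures also assume gamma-distributed thresholds and covariates unrelated to outcome. The gain from baseline adjustment (82–97%) rests on an assumed r of 0.3–0.7.

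The documents do not support a claim that all physiological endpoints miss 80% power, or that the primary analysis is affected. Severity: should-fix.

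**What to change.** 1. **Ratings, thresholds, compliance.** Replace the 10-covariate set with treatment plus the baseline value of the same measure, and at most one other prespecified covariate measured before randomisation. Baseline must replace the ten: eleven covariates leave the Cox error at 19–21%.
2. **Ratings model.** Name treatment and treatment-by-pressure in place of phenotype.
3. **Coding.** State how a censored baseline threshold, or a distension withheld after a high pain score, enters the model.
4. **Colonic transit.** Replace residual-plot selection with treatment plus baseline GC24. Add baseline GC48 for the 48-hour endpoint only if it will exist: Study Design lists baseline scans at 6–8 and 24 hours with the barostat after the 24-hour image, whereas the barostat section puts it after a 48-hour scan. These must be reconciled.
5. **Gastric emptying.** Use a baseline value only if it is collected. The Schedule of Assessments lists gastric transit at baseline, the colonic transit methods say only colonic transit is measured, and the analysis text mentions only end of treatment. Reconcile these first.

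Items 1 to 3 and the GC24 model need analysis wording only. The downside is that chance imbalance in mood, HAD or somatic symptom scores is no longer adjusted for; it can be shown descriptively.

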Secondary aims of this study are:

- #1: To describe the effect of rimegepant on rectal compliance in participants with non-constipation IBS and chronic abdominal pain.
- #2: To evaluate the effects of rimegepant on rectal sensation based on ascending method of limits and on graded rapid phasic distensions in participants with non-constipation IBS and chronic abdominal pain.
- #3: To evaluate effects of rimegepant on overall colonic transit in participants with non-constipation IBS and chronic abdominal pain.
- #4: To evaluate safety of rimegepant in participants with non-constipation IBS and chronic abdominal pain.

METHODS

STUDY INTERVENTION AND CONCOMITANT THERAPY

Rimegepant

Rimegepant (Nurtec ODT®) is an oral, small molecule, CGRP receptor antagonist approved in the US for the acute treatment of migraine and the preventive treatment of episodic migraine in adults. This is a summary of the pharmacology and dosing of rimegepant in the proposed study:

- Approved Formulation – oral dissolving tablet (ODT)
- Dosing as per Migraine Prevention: 75 mg Every Other Day (EOD) for 4 weeks/28-32 days
- Pharmacokinetics: Tmax: 1.5h; $t_{1/2}$: 11h; bioavailability: 64%
- Drug-drug Interactions: Avoid strong CYP3A4 inducers and strong or moderate CYP3A4 inhibitors
- Hepatic and Renal Impairment: Avoid use in severe hepatic impairment and end stage renal disease
- Notable Adverse Events: nausea (2.7% in rimegepant group vs 0.8% in placebo group); abdominal pain/dyspepsia (2.4% in rimegepant group vs 0.8% in placebo group)

Description of Study Drug

Rimegepant is supplied as a 75 mg white to off-white ODT in a pre-filled blister card containing 8 tablets. The placebo is supplied as a 75 mg white to off-white ODT in a pre-filled blister card containing 8 tablets. Blister cards are to be stored at 15-25°C (59-77°F).

Blinding

Participants will be blinded to their assigned study intervention. Investigators and other site staff will be blinded to participants' assigned study intervention. Participants will be assigned to receive study intervention according to the assigned treatment group from the randomization scheme. Investigators will remain blinded to each participant's assigned study intervention throughout the course of the study.

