Figure shows experimental procedure for measurement of rectal compliance by ascending method of limits (AML), sensation thresholds (indicated by arrows) and sensation ratings by random order pressure distensions and recording symptoms using 100mm visual analog scales

Ascending method of limits: compliance and sensory thresholds

Rectal sensory thresholds and compliance are measured by ramp inflation, increasing in steps of 4 mm Hg for 1 minute per step from 0 to a maximum 60 mm Hg. Thresholds for gas, first desire to defecate, urgency, and pain are indicated by the study participants by pressing a button at the distension pressure at which sensations are perceived. Ramp inflation is

terminated as soon as participants reported the first sensation of pain.

The bag is deflated and BOP is determined by pressure in the bag increased from 4 mm Hg in steps of 2 mm Hg for 1 minute per step until respiratory excursions are observed. The baseline operating pressure (BOP) set 2 mm Hg above the minimal distension pressure at which respiratory excursions are clearly recorded from the barostat tracing. Once BOP is determined there is another rest for 10 minutes.

Random order phasic distensions: sensory ratings

Phasic distensions of 12, 24, 30 and 36 mm Hg above BOP are each applied once in random order, (the order being provided before the start of the study by the biostatistician), with the participants blinded to the distension order. Each distention is maintained for 60 seconds with an interval between distensions of 2 minutes with the balloon deflated to BOP. Distension pressure is associated with intensity ratings that are generally proportional to the magnitude of the distension pressures.⁵²⁻⁵⁴ Participants mark three separate 100 mm visual analog scales (VAS) 30 seconds after the onset of the distension for the sensations of gas, urgency, and pain. These scales are anchored at each end by the descriptions 'unnoticeable' and 'unbearable'. Pressure is immediately released if the participant reported greater than 80 mm of pain on the VAS scale and higher distensions are not subsequently administered. During the assessment of sensation, the interaction between the participant and the study investigator is kept to a

minimum. Participants will also complete another VAS questionnaire to describe their sense of tiredness, peace, worry and activity before the first measurement of sensation.

Data analysis for compliance and sensory endpoints

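### The model for the phasic-distension sensory ratings tests phenotype (age, sex, BMI) and has no treatment term, so as written it does not estimate the effect of rimegepant.

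*Combined protocol and SAP*

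**What the plan says.** The second secondary aim (Hypothesis and Aims) is "To evaluate the effects of rimegepant on rectal sensation based on ascending method of limits and on graded rapid phasic distensions". The list of secondary endpoints carries the second part of that aim as item f, "Rectal sensation during random order, graded phasic distensions".

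The analysis of item f is set out once, under Statistical Analysis, B. Physiological Data, Sensory Ratings. It opens: "The assessment of phenotype associations with observed sensory ratings (rectal sensation VAS scores) will be based on analysis of covariance (ANCOVA) for repeated measures". The repeated factor is the four distension pressures. The covariates "were age, sex, BMI, the “tiredness”, “peace”, “worried”, and “activity” VAS scores, the HAD scores, and the BDQ SSC score". The remaining terms are pressure, "along with the main effect term for phenotype (e.g. age, sex, BMI), and the 2-way interaction term for phenotype by pressure". The rating scales named for separate analysis are "first sensation, gas, urgency, and pain".

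The other part of aim 2, the sensation thresholds, is handled differently: "proportional hazards regression models will be used to assess group effects separately for each of the sensation types".

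Two design facts bear on the repair. The Schedule of Assessments places the barostat study at both baseline and end of treatment. Under Random order phasic distensions, after a pain rating above 80 mm the pressure is released and "higher distensions are not subsequently administered".

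**The concern.** A model estimates only what its terms allow. With pressure, phenotype, phenotype by pressure and covariates, the fitted coefficients say how sensation ratings vary with pressure and with participant characteristics. None of them contrasts rimegepant with placebo. An analyst who followed the text would finish without a result for endpoint f.

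An analyst who noticed the gap would have to fill it unaided. The open choices are whether the drug effect is averaged over four pressures, read at 30 mmHg or tested as an interaction, and whether it is adjusted for the baseline visit. With three collected scales and four pressures, those choices should not be made after the data have been seen. The endpoint is not marginal either: the trial's title refers to visceral sensation, and the abstract predicts a reduction in rectal sensation as well as in abdominal pain.

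**Working it through.** **1. Terms in the Sensory Ratings model, against what aim 2 needs.**

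- Listed: age, sex, BMI, four state scales (tiredness, peace, worried, activity), the HAD scores and the somatic symptom score. That is ten covariates if HAD counts as two scales.
- Also listed: pressure, phenotype, and phenotype by pressure.
- Needed but absent: treatment, and treatment by pressure.
- Useful but absent: the baseline-visit rating.

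The words treatment, group, rimegepant and placebo do not occur in the paragraph.

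**2. Could another passage supply the comparison?**

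| Analysis text | Between-arm comparison named? |
|---|---|
| Colonic transit | Yes, the two treatment groups |
| Gastric emptying | Yes, active against placebo |
| Sensation thresholds | Yes, group effects |
| Phasic sensory ratings | No; phenotype is tested instead |
| Rectal compliance | None named; covariates only |

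The sentences on unpaired t-tests or rank sum tests stand under A. Clinical Data and do not reach the barostat ratings. The rectal compliance paragraph is silent on the comparison. The Sensory Ratings paragraph goes further and specifies a different question.

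**3. Was a treatment comparison intended? Reproducing the sample-size table.**

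Inputs from Sample Size: 12 per treatment group, 80% power, α = 0.05, SD 27.55 mm (pain rating at 30 mmHg) and 16.4 mm (urgency rating at 30 mmHg). Sidedness is not stated.

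For a two-sided two-sample t-test, df = 2 × 12 − 2 = 22. The detectable standardised difference d solves P(|T| > t(0.975, 22)) = 0.80, where T is noncentral t with noncentrality d × √(12/2). This gives d = 1.197.

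- Pain: 1.197 × 27.55 = 33.0 mm; the plan states 33 mm.
- Urgency: 1.197 × 16.4 = 19.6 mm; the plan states 19.6 mm.

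A normal approximation (d = 1.144) gives 31.5 and 18.8 mm, and a one-sided t-test (d = 1.048) is smaller still. Only the two-sided two-sample t-test matches. The ratings were therefore sized for a simple comparison of the two arms at 30 mmHg, and the written model contains no such comparison.

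**4. Withheld distensions (illustration only).**

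Inputs: mean 55.3 and SD 27.55 for the pain rating at 30 mmHg. The distribution is an assumption.

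- Normal: P(rating > 80) = 1 − Φ((80 − 55.3)/27.55) = 1 − Φ(0.897) = 0.185. In random order, 30 mmHg comes before 36 mmHg half the time: 0.185/2 = 0.092. That is 24 × 0.092 = 2.2 participants per visit without a 36 mmHg rating.
- The normal curve fits a 0–100 scale imperfectly: it puts 1 − Φ((100 − 55.3)/27.55) = 5% above 100 and Φ(−55.3/27.55) = 2% below 0.
- Beta on 0–100 with the same mean and SD: a + b = 0.553 × 0.447/0.2755² − 1 = 2.26, so a = 1.25 and b = 1.01. Then P(rating > 80) = 0.24, half of which is 0.12, or 2.9 participants.

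Roughly 9% to 12% of the 36 mmHg ratings would be missing at each visit, among participants who report most pain. The stop rule is not confined to one visit, so the baseline rating can be missing for the same reason.

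**The case against.** The strongest reply is that the plan does intend this comparison and that *phenotype* is a label carried over for the group factor. Aim 2 speaks of the effects of rimegepant, endpoint f is listed, and the table is per treatment group. The threshold analysis reuses the same covariates and names group effects. Age, sex and BMI are already covariates, so a phenotype term made of the same three variables would be redundant, and the examples are only examples.

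The part about intent stands. A reader might infer that the sponsor chose not to test the drug on phasic sensation, or that no valid test is possible. The documents support neither: the comparison was sized, and the randomised data to make it are collected. The part about wording does not rescue the model. Nothing defines phenotype as treatment, and every example given is a participant characteristic. Intent also does not settle the contrast or the baseline adjustment.

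A reader might also infer that the participants with most pain will be dropped from the analysis. The plan does not state a complete-case analysis, and because the order is random, a rating above 80 mm costs only the higher levels not yet applied. The harm is conditional on how the model is fitted.

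Lack of baseline adjustment affects precision, not the validity of a randomised comparison. This is also one of eight listed secondary endpoints in a pilot; the primary endpoint and trial conduct are untouched.

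**Conclusion.** The Sensory Ratings model is wrong as written. It addresses phenotype associations and has no term for treatment or treatment by pressure, so it yields no estimate of the drug effect for endpoint f or for the phasic-distension part of aim 2. The threshold part of the aim is not affected. The conclusion rests on the model terms alone and needs no numerical assumption.

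The reproduced 33 mm and 19.6 mm confirm that a comparison of the arms was planned, which makes this an error of specification and not an omission by design. The figure of about 9% to 12% for withheld 36 mmHg ratings depends on an assumed distribution. It is a reason to choose the model carefully, not a finding in itself.

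**What to change.** In Sensory Ratings:

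- Replace the phenotype and phenotype-by-pressure terms with treatment and treatment by pressure.
- Name one main treatment contrast in advance, reported with a 95% CI: either averaged over the four pressures, or at 30 mmHg to match the sizing. Either is defensible.
- Adjust for the baseline-visit ratings. A same-pressure baseline covariate can itself be missing under the stop rule, and rows without it would be lost. Modelling baseline and end-of-treatment ratings jointly avoids this.
- Fit a likelihood-based mixed model with participant as the repeated unit, so that a participant with distensions withheld at either visit still contributes the ratings obtained.

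Whether to keep the other covariates is a separate choice that the sponsor should state. All ten plus treatment leave 24 − 1 − 1 − 10 = 12 between-participant degrees of freedom. Power at 33 mm then falls from 80.1% to 76.8% through that loss alone, before any gain from variance explained or loss from chance imbalance.

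As clean-up, delete the first-sensation rating scale (only gas, urgency and pain are marked during phasic distensions) and, under Rectal compliance, fasting colonic tone, which no described procedure measures. Name the treatment comparison there too.

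The cost is wording in the analysis section. The ratings at both visits are already in the schedule. The change should be dated before unblinding.
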